6.6.5. Laboratory data

6.6.5.1. Hematology and chemistry parameters

Laboratory results will be classified according to the NCI-CTCAE criteria version 4.03. Non-numerical qualifiers (with the exception of fasting flags) will not be taken into consideration in the derivation of CTCAE criteria (eg, hypokalemia Grade 1 and Grade 2 are only distinguished by a non-numerical qualifier and therefore Grade 2 will not be derived). Additional laboratory results that are not part of NCI-CTCAE will be presented according to the categories: below normal limit, within normal limits and above normal limit (according to the laboratory normal ranges).

Quantitative data will be summarized using simple descriptive statistics (mean, SD, median, Q1, Q3, minimum, and maximum) of actual values and changes from baseline for each nominal visit over time (unscheduled measurements would therefore not be included in these summaries as described in Section 5.2.9). End of Treatment visit laboratory results will be summarized separately. The changes computed will be the differences from baseline. Qualitative data based on reference ranges will be described according to the categories (ie, Low, Normal, High).

Abnormalities classified according to NCI-CTCAE toxicity grading version 4.03 will be described using the worst grade. For those parameters which are graded with two toxicities such as potassium (hypokalemia/hyperkalemia), the toxicities will be summarized separately. Low direction toxicity (eg, hypokalemia) grades at baseline and post baseline will be set to 0 when the variables are derived for summarizing high direction toxicity (eg, hyperkalemia), and vice versa.

For **WBC differential counts** (total neutrophil [including bands], lymphocyte, monocyte, eosinophil, and basophil counts), the absolute value will be used when reported. When only percentages are available (this is mainly important for neutrophils and lymphocytes, because the CTCAE grading is based on the absolute counts), the absolute value is derived as follows:

$$\text{Derived differential absolute count} = (\text{WBC count}) \times (\text{Differential \%value} / 100)$$

If the range for the differential absolute count is not available (only range for value in % is available) then Grade 1 will be attributed to as follows:

- Lymphocyte count decreased:
 - derived absolute count does not meet Grade 2-4 criteria, and
 - % value < % LLN value, and
 - derived absolute count $\geq 800/\text{mm}^3$
- Neutrophil count decreased
 - derived absolute count does not meet Grade 2-4 criteria, and
 - % value < % LLN value, and

- derived absolute count $\geq 1500/\text{mm}^3$

For **calcium**, CTCAE grading is based on Corrected Calcium and Ionized Calcium (CALCIO). Corrected Calcium is calculated from Albumin and Calcium as follows

$$\text{Corrected calcium (mmol/L)} = \text{measured total Calcium (mmol/L)} + 0.02 (40 - \text{serum albumin [g/L]})$$

Liver function tests: Alanine aminotransferase (ALT), aspartate aminotransferase (AST), and total bilirubin (TBILI) are used to assess possible drug induced liver toxicity. The ratios of test result over upper limit of normal (ULN) will be calculated and classified for these three parameters during the on-treatment period.

Summary of liver function tests will include the following categories. The number and percentage of patients with each of the following during the on-treatment period will be summarized by treatment arm:

- ALT $\geq 3 \times \text{ULN}$, ALT $\geq 5 \times \text{ULN}$, ALT $\geq 10 \times \text{ULN}$, ALT $\geq 20 \times \text{ULN}$
- AST $\geq 3 \times \text{ULN}$, AST $\geq 5 \times \text{ULN}$, AST $\geq 10 \times \text{ULN}$, AST $\geq 20 \times \text{ULN}$
- (ALT or AST) $\geq 3 \times \text{ULN}$, (ALT or AST) $\geq 5 \times \text{ULN}$, (ALT or AST) $\geq 10 \times \text{ULN}$, (ALT or AST) $\geq 20 \times \text{ULN}$
- TBILI $\geq 2 \times \text{ULN}$
- Concurrent ALT $\geq 3 \times \text{ULN}$ and TBILI $\geq 2 \times \text{ULN}$
- Concurrent AST $\geq 3 \times \text{ULN}$ and TBILI $\geq 2 \times \text{ULN}$
- Concurrent (ALT or AST) $\geq 3 \times \text{ULN}$ and TBILI $\geq 2 \times \text{ULN}$
- Concurrent (ALT or AST) $\geq 3 \times \text{ULN}$ and TBILI $\geq 2 \times \text{ULN}$ and ALP $> 2 \times \text{ULN}$
- Concurrent (ALT or AST) $\geq 3 \times \text{ULN}$ and TBILI $\geq 2 \times \text{ULN}$ and (ALP $\leq 2 \times \text{ULN}$ or missing)

Concurrent measurements are those occurring on the same date.

Categories will be cumulative, ie, a patient with an elevation of AST $\geq 10 \times \text{ULN}$ will also appear in the categories $\geq 5 \times \text{ULN}$ and $\geq 3 \times \text{ULN}$. Liver function elevation and possible Hy's Law cases will be summarized using frequency counts and percentages.

An evaluation of Drug-Induced Serious Hepatotoxicity (eDISH) plot will also be created, with different symbols for different treatment arms, by graphically displaying

- peak serum ALT(/ULN) vs peak total bilirubin (/ULN) including reference lines at ALT=3×ULN and total bilirubin=2×ULN.
- peak serum AST(/ULN) vs peak total bilirubin (/ULN) including reference lines at AST=3×ULN and total bilirubin=2×ULN.

In addition, a listing of all TBILI, ALT, AST and ALP values for patients with a post-baseline TBILI $\geq 2 \times \text{ULN}$, ALT $\geq 3 \times \text{ULN}$ or AST $\geq 3 \times \text{ULN}$ will be provided.

Parameters with NCI-CTC grades available:

The laboratory toxicities will be tabulated using descriptive statistics (number of patients and percentages) during the on-treatment period. The denominator to calculate percentages for each laboratory parameter is the number of patients evaluable for CTCAE grading (ie those patients for whom a Grade 0, 1, 2, 3 or 4 can be derived).

- The summary of laboratory parameters by CTCAE grade table will include number and percentage of patients with Grade 1, 2, 3, 4, Grade 3/4 and any grade (Grades 1-4), laboratory abnormalities during the on-treatment period.
- The shift table will summarize baseline CTCAE grade versus the worst on-treatment CTCAE grade. The highest CTCAE grade during the on-treatment period is considered as the worst grade for the summary.
- The number and percentage of patients with newly occurring or worsening laboratory abnormalities during the on-treatment period will be summarized by worst grade on-treatment (Grade 1, 2, 3, 4, Grade 3/4 and any grade (Grades 1-4)).

The above analyses apply to hematology and chemistry evaluations which can be graded per CTCAE, ie:

- Hematology:
Hemoglobin (HB), Leukocytes (white blood cell decreased), Lymphocytes (lymphocyte count increased/decreased), Neutrophils / Absolute Neutrophils Count (ANC) (neutrophil count decreased), Platelet Count (PLT) (platelet count decreased).
- Serum Chemistry:
Albumin (hypoalbuminemia), Alkaline Phosphatase (alkaline phosphatase increased), Alanine Aminotransferase (ALT) (ALT increased), Amylase (serum amylase increased), Aspartate Aminotransferase (AST) (AST increased), Total Bilirubin (blood bilirubin increased, Cholesterol (cholesterol high), Creatinine (creatinine increased), Creatine Kinase (CPK increased), Potassium (hypokalemia/ hyperkalemia), Sodium (hyponatremia/ hypernatremia), Magnesium (hypomagnesemia/hpermagnesemia), Calcium (hypocalcemia/ hypercalcemia), Glucose (hypoglycemia/hyperglycemia), Gamma Glutamyl Transferase (GGT) (GGT increased), Lipase (lipase increased), Phosphates (hypophosphatemia), Triglycerides (hypertriglyceridemia).

Parameters with NCI-CTC grades not available:

Hematology and chemistry evaluations which cannot be graded per CTCAE criteria will be summarized as frequency (number and percentage) of patients with:

- shifts from baseline normal to at least one result above normal during on-treatment period

- shifts from baseline normal to at least one result below normal during on-treatment period

In this study, these apply to the following parameters:

- Thyroid function and ACTH tests: Free T4, Thyroid Stimulating Hormone (TSH), ACTH

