5. Evidence of a signed and dated informed consent document indicating that the patient (or a legally acceptable representative, as allowed by local guideline/practice) has been informed of all pertinent aspects of the study.

6. Patients who are willing and able to comply with scheduled visits, treatment plans, laboratory tests, and other study procedures.
7. Age ≥ 18 years (≥ 20 years in Japan).
8. Estimated life expectancy of at least 3 months.
9. Eastern Cooperative Oncology Group (ECOG) performance status (PS) 0 or 1 ([Appendix 1](#)).
10. Adequate bone marrow function, including:
 - a. Absolute neutrophil count (ANC) $\geq 1,500/\text{mm}^3$ or $\geq 1.5 \times 10^9/\text{L}$;
 - b. Platelets $\geq 100,000/\text{mm}^3$ or $\geq 100 \times 10^9/\text{L}$;
 - c. Hemoglobin ≥ 9 g/dL (may have been transfused).
11. Adequate renal function, defined as estimated creatinine clearance ≥ 30 mL/min as calculated using the Cockcroft-Gault equation ([Appendix 4](#)) or by 24-hour urine collection for creatinine clearance or according to the local institutional standard method.
12. Adequate liver function, including:
 - a. Total serum bilirubin ≤ 1.5 x upper limit of normal (ULN);
 - b. Aspartate aminotransferase (AST) and alanine aminotransferase (ALT) ≤ 2.5 x ULN, or, for patients with documented metastatic disease to the liver, AST and ALT levels $\leq 5 \times$ ULN.
13. Serum pregnancy test (for females of childbearing potential) negative at screening.
14. Female patients of childbearing potential and at risk for pregnancy must agree to use a highly effective method of contraception ([Section 4.3.1](#)) throughout the study and for at least 30 days after the last dose of assigned treatment.

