8.6.2. Potential Cases of Drug-Induced Liver Injury

Abnormal values in aspartate aminotransferase (AST) and/or alanine aminotransferase (ALT) concurrent with abnormal elevations in total bilirubin that meet the criteria outlined below in the absence of other causes of liver injury are considered potential cases of drug-induced liver injury (potential Hy's law cases) and should always be considered important medical events.

The threshold of laboratory abnormalities for a potential case of drug-induced liver injury depends on the patient's individual baseline values and underlying conditions. Patients who

present with the following laboratory abnormalities should be evaluated further to definitively determine the etiology of the abnormal laboratory values:

- Patients with AST or ALT and total bilirubin baseline values within the normal range who subsequently present with AST or ALT values ≥ 3 times the upper limit of normal (\times ULN) concurrent with a total bilirubin value $\geq 2 \times$ ULN with no evidence of hemolysis and an alkaline phosphatase value $\leq 2 \times$ ULN or not available.
- For patients with preexisting ALT **OR** AST **OR** total bilirubin values above the ULN, the following threshold values should be used in the definition mentioned above:
 - For patients with preexisting AST or ALT baseline values above the normal range, AST or ALT value ≥ 2 times the baseline values and $\geq 3 \times$ ULN, or $\geq 8 \times$ ULN (whichever is smaller).
- **Concurrent with**
 - For patients with preexisting values of total bilirubin above the normal range: Total bilirubin increased from baseline by an amount of at least $1 \times$ ULN **or** if the value reaches $\geq 3 \times$ ULN (whichever is smaller).

The patient should return to the investigational site and be evaluated as soon as possible, preferably within 48 hours from awareness of the abnormal results. This evaluation should include laboratory tests, detailed history and physical assessment. The possibility of hepatic neoplasia (primary or secondary) should be considered.

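### The SAP's possible Hy's Law count uses fixed ULN cut-offs and leaves out the protocol's thresholds for patients whose liver tests are above normal at baseline

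*SAP*

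**What the plan says.** **SAP 6.6.5.1 (liver function tests).** For ALT, AST and total bilirubin, "The ratios of test result over upper limit of normal (ULN) will be calculated and classified for these three parameters during the on-treatment period". The single-enzyme rows start at 3 × ULN and continue at 5, 10 and 20 × ULN. The combined rows need ALT or AST ≥3 × ULN together with bilirubin ≥2 × ULN, and the last of them adds ALP ≤2 × ULN or missing. On timing, "Concurrent measurements are those occurring on the same date". The section then says that possible Hy's "Law cases will be summarized using frequency counts and percentages". It gives no other definition of such a case and does not refer to Protocol 8.6.2.

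**Protocol 8.6.2.** "The threshold of laboratory abnormalities for a potential case of drug-induced liver injury depends on the patient's individual baseline values". The normal-baseline branch has the same numbers and the same ALP condition as the SAP's last row. Where a liver test was already abnormal at baseline, the protocol states that "the following threshold values should be used in the definition mentioned above". Two rules are then given, one per analyte group:

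- Transaminases: the clause that opens "For patients with preexisting AST or ALT baseline values above the normal range, AST or ALT value" sets the threshold at twice baseline and no lower than 3 × ULN, or at 8 × ULN if that is smaller.
- Bilirubin: the wording is "Total bilirubin increased from baseline by an amount of at least", and the amount is 1 × ULN; a value of 3 × ULN serves instead if that is smaller.

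**Protocol 4.1, inclusion criterion 12.** Bilirubin may be up to 1.5 × ULN. AST and ALT may be up to 2.5 × ULN, but "for patients with documented metastatic disease to the liver, AST and ALT levels" may be up to 5 × ULN.

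**The concern.** The SAP reproduces one branch of a two-branch definition and uses the same Hy's Law label. The omitted branch covers patients whom the eligibility criteria admit on purpose, chiefly those with liver metastases. For them the transaminase half of a SAP case may have been present before treatment. Hy's Law counts get close attention in any safety review. Here one study would produce two differently defined sets of cases under one name, with nothing in the SAP to reconcile them.

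**Working it through.** The plan states no figure to reproduce, so the two rules are compared directly. All values are multiples of ULN, b is the baseline value, and each analyte is judged against its own baseline.

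**Rules**

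- SAP: ALT/AST ≥3 and bilirubin ≥2, whatever b is.
- Protocol, ALT/AST: 3 if b ≤1; otherwise min(max(2b, 3), 8).
- Protocol, bilirubin: 2 if b ≤1; otherwise min(b + 1, 3).

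**Thresholds over the eligible range**

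| Analyte | Baseline | Protocol | SAP |
|---|---|---|---|
| ALT/AST | 1.2 | max(2.4, 3) = 3.0 | 3.0 |
| ALT/AST | 2.0 | 4.0 | 3.0 |
| ALT/AST | 2.5 | 5.0 | 3.0 |
| ALT/AST | 3.0 | 6.0 | 3.0 |
| ALT/AST | 4.0 | 8.0 | 3.0 |
| ALT/AST | 5.0 | min(10, 8) = 8.0 | 3.0 |
| Bilirubin | 1.2 | 2.2 | 2.0 |
| Bilirubin | 1.4 | 2.4 | 2.0 |
| Bilirubin | 1.5 | 2.5 | 2.0 |

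The ALT/AST rules part once b exceeds 1.5, where 2b passes 3. The bilirubin rules part as soon as b exceeds 1.

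**Direction.** The protocol's ALT/AST threshold is never below 3 and its bilirubin threshold is never below 2. Any pair that meets the protocol's thresholds therefore meets the SAP's. A grid of 84,835 combinations of baseline and on-treatment values agrees: none met the protocol and missed the SAP, and 13,889 met the SAP and missed the protocol. Those are grid points, not an estimate of patients.

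**Two examples, ALP ≤2**

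- ALT 4.0 to 4.5 and bilirubin 1.4 to 2.0. SAP: 4.5 ≥3 and 2.0 ≥2, a case. Protocol: needs 8.0 and 2.4, not a case.
- ALT unchanged at 4.0 and bilirubin 1.0 to 2.0. SAP: a case. Protocol: ALT is short of 8.0, not a case.

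**Can unchanged values make a Hy's Law case?** No. The highest eligible bilirubin is 1.5, so a rise of at least 2.0 − 1.5 = 0.5 is needed. No eligible unchanged pair in the grid qualified.

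**Single-enzyme rows.** A patient with liver metastases who enters at 3 to 5 and does not change is counted in the ≥3 row, and at exactly 5 also in the ≥5 row. Without liver metastases the entry cap is 2.5, so an unchanged value is not counted.

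**The case against.** The best defence is that Protocol 8.6.2 governs the work-up and SAE reporting of individual cases. Protocol 9.5 asks only for worst-grade frequencies and shift tables, and the SAP supplies both. That is correct, and it rules out saying that the protocol requires its definition in the tables. But the SAP chose to count possible Hy's Law cases, and the reader needs to know which definition applies.

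It can also be said that baseline is already handled. SAP 6.6.5.1 plans shift tables from baseline grade to worst grade, tables of newly occurring or worsening abnormalities, and a listing of all liver values for flagged patients. For single enzymes this largely succeeds: a patient who stays at 4 × ULN appears as unchanged. It does not settle the combined count, for three reasons:

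- The grade tables take one analyte at a time.
- The grades are coarse. Under the bands in Protocol Table 5, ALT moving from 4 to 5.5 and from 4 to 8 both end above 5 × ULN, yet only the second doubles baseline.
- The listing allows manual review but defines no case, and the eDISH plot has ULN reference lines only.

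A reader might go further and infer that the SAP count can only exceed the cases reported as SAEs. The documents do not support that. SAP 5.2.7 ends the on-treatment period at 30 days after last dose (for Arm B, after the end of BSC), or sooner if new anti-cancer drug therapy starts. Protocol 8.2 runs SAE reporting to 90 days (for Arm B, from the EOT visit). The SAP also requires same-date values, where the protocol says only concurrent. A protocol case can therefore be missing from the SAP table.

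**Conclusion.** The point holds as a mismatch of definitions. For patients whose baseline ALT or AST exceeds 1.5 × ULN, or whose bilirubin exceeds ULN, the SAP's Hy's Law thresholds are looser than the protocol's, by up to 5 × ULN for transaminases (8 against 3) and 0.5 × ULN for bilirubin (2.5 against 2.0).

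Two stronger readings are tempting and fail:

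- That patients with liver metastases become Hy's Law cases through pre-existing elevations. Only the transaminase part can be pre-existing, because bilirubin must newly rise to 2 × ULN.
- That the SAP attributes these elevations to treatment. The rows are descriptive counts by arm and make no claim of relatedness.

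The number of patients affected cannot be computed. The documents do not give the share with liver metastases or with raised baseline values. The conclusion assumes that the eligibility limits still hold at the safety baseline, that possible Hy's Law cases means the SAP's combined rows, and that a patient with only one analyte raised keeps the normal-baseline threshold for the other. It is worth correcting because it changes a reported safety count, but it does not touch the efficacy analysis.

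**What to change.** In SAP 6.6.5.1:

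1. Add one derived row or flag for potential Hy's Law cases that applies both laboratory branches of Protocol 8.6.2, chosen by baseline AST/ALT and bilirubin status. State the rule for patients with only one analyte raised.
2. Keep the existing fixed-ULN rows and label them as unadjusted screening counts.
3. State that the new count need not equal the SAE-reported cases. Those also require confirmation on repeat testing and no other identified cause (Protocol 8.6.2), and they follow the 90-day reporting window.

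The cost is one derivation and one extra table row. The safety baseline is already defined in SAP 3.4.1 and the laboratory values are already collected, so no new data are needed.

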| Laboratory Studies | | | | | |
| Coagulation ⁸ | X | X | X | X | |
| Hematology ⁸ | X | X | X | X | |
| Blood Chemistry (full and core) ^{8,9} | X | X ^{8,9} | X ^{8,9} | X ^{8,9} | |
| Thyroid Function and ACTH Tests ¹⁰ | X | X (at Cycles 3, 5, 7, etc.) | | X (at Cycles 3, 5, 7, etc.) | |
| Serum/Urine Pregnancy Test ¹¹ | X | X | X | | |
| Troponin ¹² | X | X (Cycles 1-4 and as clinically indicated) | X (Cycles 1-3 and as clinically indicated) | X (Cycles 1-4 and as clinically indicated) | |
| HBV, HCV Tests | X | If clinically indicated | | If clinically indicated | |
| HIV test ¹³ | X | | | | |
| Urinalysis ¹⁴ | X | If clinically indicated | | If clinically indicated | |
| 12-Lead ECG ¹⁵ | X | If clinically indicated | | If clinically indicated | |
| Disease Assessments | | | | | |
| Tumor Assessments (including scans) ¹⁶ | X | X (Q8W for the 1 st yr after randomization and Q12W thereafter) | | X (Q8W for the 1 st yr after randomization and Q12W thereafter) | |
| Other Clinical Assessments | | | | | |
| Adverse Events ¹⁷ | | X | X | X | X ¹⁸ |
| Concomitant Medications/Treatments ¹⁹ | X | X | X | X | X ¹⁸ |

| Visit Identifiers ¹ | Screening | Study Treatment (1 cycle = 4 weeks) | | | |
|--|-----------|---|---|--------------------------------|---|
| | | Arm A | | Arm B | |
| | | Within 28 Days Prior to Randomization | Cycle 1 Day 1 Cycle ≥2 Day 1 (±3 days) | Day 15 (±3 days) All Cycles | Cycle 1 Day 1 Cycle ≥2 Day 1 (±3 days) |
| Patient Reported Outcomes (NCCN-FACT FBISI-18, EQ-5D-5L) ²⁰ | | X | | X | |
| Randomization & Study Treatment | | | | | |
| Randomization ²¹ | X | | | | |
| Avelumab (Arm A only) ²² | | X | X | | |
| Best Supportive Care (BSC) ²³ | | X (Throughout study treatment) | | X (Throughout study treatment) | |
| Other Samplings | | | | | |
| Archival FFPE Tumor Tissue ²⁴ | X | | | | |
| Mandatory Recent FFPE Tumor Tissue Block or de novo biopsy ²⁵ | X | | | | |
| Banked Blood Biospecimen for Genotyping ²⁶ | | X (Cycle 1 only) | | X (Cycle 1 only) | |
| Banked Blood Biospecimens for Exploratory Assessments ²⁷ | | X (Cycle 1, 2, 3 & 5) | X (Cycle 1 only) | X (Cycle 1, 2, 3 & 5) | |
| Pharmacokinetics ²⁸ | | X (Cycles 1-3, 5, 7, 9, 11 & 13) | X (Cycles 1-3) | | |
| Anti-Avelumab Antibodies and Neutralizing Antibodies ²⁹ | | X (Cycles 1-3, 5, 7, 9, 11 & 13) | X (Cycles 1-3) | | |

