| 7. | Contraception Check: Female patients who are of childbearing potential will need to affirm that they meet the criteria for correct use of the selected methods of contraception. The investigator or his or her designee will discuss with the patient the need to use the selected contraception methods consistently and correctly and document such conversations in the patient's chart. In addition, the investigator or his or her designee will instruct the patient to call immediately if the selected contraception methods are discontinued, or if pregnancy is known or suspected in the patient or the male patient's partner. After randomization, contraception checks will be performed only for Arm A patients. See Section 4.3.1 . |
| 8. | Coagulation, Hematology, and Blood Chemistry (full panel): Required tests are listed in Table 6 . Full chemistry panel is required at Screening, Cycle 1 Day 1, Cycle 1 Day 15 (Arm A patients), Cycle 2 Day 1, Cycle 3 Day 1, and Day 1 of every 2 cycles (8 weeks) thereafter. May also be performed when clinically indicated. If full and core chemistry panels are scheduled at the same visit, only the full chemistry will be performed. |
| 9. | Blood Chemistry (core panel): Core chemistry panel (required tests are listed in Table 6) is required at each clinic visit at which a full chemistry panel is not required. |
| 10. | Thyroid Function and ACTH Tests: Free T4, TSH, and ACTH tests will be performed at screening, Cycle 3 Day 1, and Day 1 of every 2 cycles (8 weeks) thereafter. Additional tests should be performed when clinically indicated. See Table 6 . |

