| 
If a patient begins a new anticancer therapy, the AE reporting period for non-serious AEs ends at the time the new treatment is started. Death must be reported if it occurs during the SAE reporting period after the last dose of study treatment, irrespective of any intervening treatment.
 |
| 
18. Day 15 Assessments for Arm B: Remote contact (eg, telephone) or in-clinic visit for collection of interim AEs and changes in concomitant medications and treatments, if any. A follow-up in-clinic visit should be scheduled if clinically indicated.
 |
| 
19. Concomitant Medications/Treatments: Concomitant medications and treatments will be recorded for all patients from 28 days prior to the start of study treatment and up to 90 days after the last dose of study treatment (Arm A) or 90 days after the EOT visit (Arm B). If a patient begins a new anti-cancer therapy, reporting of concomitant medications should end at the time the new cancer therapy is started; see Section 5.9 for additional details. All concomitant medications will be recorded in the CRF including supportive care drugs (eg, anti-emetic treatment and prophylaxis), the drugs used to treat adverse events or chronic diseases, and non-drug supportive interventions (eg, transfusions). Concomitant medications should be reviewed at each study visit, and any prohibited treatments (as described in Section 5.9) should be discussed with the patient and appropriately managed.
 |
| 
20. NCCN-FACT FBISI-18, EQ-5D-5L: All patients will complete these self-administered questionnaires on Day 1 of each cycle. Patients must complete each questionnaire at the clinic prior to any study or medical procedure.
 |
| 
21. Randomization: An interactive response technology (IRT) system will be used for randomization to a treatment arm as described in Section 5.1. Patients meeting all entry criteria will be randomized and, if randomized to Arm A, will be administered the first dose of avelumab within 3 days after randomization.
 |

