3.2. Secondary Endpoints

3.2.1. Safety endpoints

- Adverse events (AEs) and laboratory abnormalities as graded by National Cancer Institute (NCI) Common Terminology Criteria for Adverse Events (CTCAE) v4.03; vital signs (blood pressure, pulse rate).

AEs will be graded by the investigator according to CTCAE v4.03 and coded using the Medical Dictionary for Regulatory Activities (MedDRA).

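### Hematology and core chemistry are drawn about twice as often in Arm A as in Arm B, so the SAP's by-arm worst-grade and liver tables are expected to show more abnormalities in Arm A even with no drug effect

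*SAP*

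**What the plan says.** **Sampling schedule.** In the protocol's Schedule of Activities for the screening and treatment periods (before Amendment 6), the hematology row reads "Hematology ⁸ | X | X | X | X". The four marks are screening, Arm A Day 1, Arm A Day 15 and Arm B Day 1; Arm B Day 15 is blank. The coagulation and blood chemistry rows follow the same pattern. Footnote 18 describes the Arm B Day 15 contact as "Remote contact (eg, telephone) or in-clinic visit for collection of interim AEs and changes in concomitant medications and treatments, if any", so no routine blood draw is planned then.

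Chemistry has two panels, defined in Table 6 of protocol Section 7.1.3:

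- **Core panel** (footnote 9): "is required at each clinic visit at which a full chemistry panel is not required". That means twice per cycle in Arm A and once in Arm B.
- **Full panel** (footnote 8): "Full chemistry panel is required at Screening, Cycle 1 Day 1, Cycle 1 Day 15 (Arm A patients), Cycle 2 Day 1", then Cycle 3 Day 1 and every second cycle. Arm A's only extra panel is at Cycle 1 Day 15.

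Thyroid and ACTH tests (footnote 10) are on one schedule for both arms: "Free T4, TSH, and ACTH tests will be performed at screening, Cycle 3 Day 1" and every second cycle after that.

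**Analysis.** SAP 3.2.1 makes "laboratory abnormalities as graded by National Cancer Institute (NCI) Common Terminology Criteria for Adverse Events (CTCAE) v4.03" a secondary safety endpoint. SAP 6.6.5.1 specifies tables of grade, shift from baseline to worst grade, newly occurring or worsening abnormalities, and ALT/AST/bilirubin threshold categories. For the shift table it states: "The highest CTCAE grade during the on-treatment period is considered as the worst grade for the summary". SAP 6.6 presents safety summaries by arm. SAP 5.2.9 brings unscheduled results into the analyses and restricts only the by-visit descriptive statistics to scheduled visits. The SAP has no table limited to common visits, no allowance for number of samples, and no caveat.

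**The concern.** A patient enters these tables if any on-treatment result reaches the grade or threshold. The denominator is evaluable patients, so the number of looks per patient matters. With the same underlying biology in both arms, an abnormality that rises and settles between two monthly draws can be missed in Arm B and caught by an Arm A Day 15 draw.

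The parameters sampled most unequally include the liver tests, so the Hy's law categories and the eDISH plots of peak values are affected as well as the hematology grades. Readers judge laboratory toxicity from side-by-side percentages. A gap that partly reflects ascertainment would be read as an effect of avelumab, and a small real difference could not be told apart from it.

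**Working it through.** The documents give no expected rate of laboratory abnormalities, so there is no planned figure to reproduce. Per-sample risk, number of cycles, within-patient correlation and episode length below are assumptions.

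**1. Parameters affected.** SAP 6.6.5.1 lists 5 hematology and 18 chemistry parameters with CTCAE grades, 23 in all. Table 6 marks 11 of the 18 as core: ALT, AST, ALP, bilirubin, creatinine, sodium, potassium, magnesium, calcium, glucose and phosphate. So 5 + 11 = 16 follow the Day 1 and Day 15 pattern. Calcium is graded on an albumin-corrected value and albumin is full-panel only, so its extra gradings may be fewer. The remaining 7 are full-panel only: albumin, amylase, cholesterol, creatine kinase, GGT, lipase and triglycerides.

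**2. Scheduled samples after baseline.** Take Cycle 1 Day 1 as baseline, k cycles in both arms, and add the End of Treatment and 30-day visits.

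- Hematology and core chemistry, Arm A: (k−1) Day 1 draws + k Day 15 draws + 2
- Hematology and core chemistry, Arm B: (k−1) + 2
- Result: 7 vs 4 at 3 cycles, 13 vs 7 at 6 cycles, 25 vs 13 at 12 cycles
- Full-panel-only analytes at 6 cycles: Day 1 of Cycles 2, 3 and 5, plus 2, gives 5 in Arm B; Cycle 1 Day 15 makes 6 in Arm A
- Thyroid and ACTH at 6 cycles: 4 vs 4

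**3. No drug effect, independent samples.** P(at least one abnormal) = 1 − (1−p)^n, where p is the risk per sample. At 6 cycles:

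| p | Arm A (n=13) | Arm B (n=7) | Ratio |
|---|---|---|---|
| 0.5% | 6.3% | 3.4% | 1.83 |
| 1% | 1 − 0.99^13 = 12.2% | 1 − 0.99^7 = 6.8% | 1.80 |
| 2% | 23.1% | 13.2% | 1.75 |
| 5% | 48.7% | 30.2% | 1.61 |

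For full-panel-only analytes at p = 1%: 1 − 0.99^6 = 5.9% vs 1 − 0.99^5 = 4.9%, ratio about 1.2.

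**4. No drug effect, correlated samples.** This is a simulation with a patient random effect (ICC) plus a two-week autoregressive term (AR), at 6 cycles and p = 1%.

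| ICC, AR | Arm A | Arm B | Ratio |
|---|---|---|---|
| 0.5, 0.5 | 6.8% | 4.8% | 1.42 |
| 0.8, 0.8 | 3.1% | 2.7% | 1.16 |
| 0.95, 0.9 | 1.6% | 1.5% | 1.06 |

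**5. By episode length.** A randomly timed episode of L weeks is detected with probability min(1, L/2) on two-weekly draws and min(1, L/4) on four-weekly draws: 50% vs 25% for 1 week, 100% vs 50% for 2 weeks, 100% vs 75% for 3 weeks, and 100% in both arms from 4 weeks on.

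**6. Common time points only.** Dropping Day 15 leaves 7 vs 7 samples at 6 cycles, so 6.8% vs 6.8% at p = 1%, given equal time on treatment.

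**The case against.** **These are descriptive tables.** This stands. No test or between-arm difference is planned for laboratory data; SAP 6.6.4 limits risk differences to irAEs and Tier-2 events, and SAP 3.5.1 treats safety analyses as generally exploratory. No error rate is at stake, only how side-by-side percentages are read.

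**Matched-visit information already exists.** This stands in part. The by-visit summaries give quartiles, minimum and maximum as well as means, so some view of the tails at Day 1 visits is available. They do not give the proportion of patients with graded abnormalities.

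**The effect may be small.** This also stands. For stable analytes the ratio is close to 1.

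**A reader might infer that all laboratory testing is doubled in Arm A.** The documents do not support that. Lipase and amylase, for example, have one extra Arm A sample. Troponin and coagulation are sampled more often in Arm A, but SAP 6.6.5.2 only lists them, so they enter no worst-grade table.

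**A reader might also infer that Arm A must show more abnormalities, or about twice as many.** That is an expectation whose size depends on quantities the documents do not give.

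**Closer sampling of treated patients may be clinically appropriate.** The visit schedule is not questioned here.

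**Conclusion.** The point holds for hematology and core chemistry. With identical biology and equal time on treatment, the planned by-arm tables are expected to show more abnormalities in Arm A. At 6 cycles and an assumed 1% risk per sample, the ratio runs from 1.80 with independent samples down to 1.06 under strong within-patient correlation. Short-lived abnormalities drive the gap. It is slight for the seven full-panel-only analytes and absent, on scheduled samples, for thyroid and ACTH tests. Unscheduled draws and any difference in treatment duration lie outside these figures. Neither OS nor any formal test is touched. This is a cheap improvement to a secondary safety display, worth making because the SAP neither adjusts for the unequal schedule nor mentions it.

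**What to change.** Keep the planned all-samples tables in SAP 6.6.5.1 as the full safety record, with unscheduled results. These include the repeat liver tests that protocol Section 8.6.2 requires for potential Hy's law cases.

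Add a supplementary by-arm set for hematology and core chemistry: worst grade, shift, newly occurring or worsening, and liver thresholds. Limit it to baseline and time points scheduled in both arms, namely Day 1 visits, End of Treatment, and the 30-day visit where it falls within the on-treatment period.

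Footnote the all-samples tables to say that Arm A was also sampled on Day 15. State in the supplementary set that any difference in time on treatment remains, since SAP 5.2.7 ends the window with each patient's own treatment or a new anti-cancer drug.

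**Cost.** A visit filter on data already collected and one more set of descriptive tables. Abnormalities seen only on Arm A Day 15 or at unscheduled draws will not appear in the supplementary set, but they stay in the main tables.
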